5.5 Handling of Missing Data

Missing data will not be imputed from analyses.

Protocol 405-201-00055 Statistical Analysis Plan

6 Primary and Secondary Outcome Variables:

6.1 Primary Outcome Variables

The primary outcome variable is four-week continuous smoking abstinence rate during Week 4 to Week 7.

6.2 Secondary Outcome Variables

Secondary outcome variable is the incidence of nausea at any timepoint after drug administration begins.

7 Disposition and Demographic Analysis

7.1 Subject Disposition

Subject disposition will be summarized by center.

Subject completion rate and reasons for discontinuation will be summarized for the enrolled analysis set.

7.2 Demographic and Baseline Characteristics

Baseline demographic characteristics include age, sex, race, ethnicity, height, weight, and BMI. For the enrolled analysis set, demographic characteristics will be summarized.

Mean, range and standard deviation will be used to describe continuous variables such as age. Frequency distributions will be tabulated for categorical variables such as race.

Baseline value is defined as the value at baseline visit (Day -1), if the value at the baseline visit is not available, the baseline value will be last evaluable assessment prior to the first dose of IMP.

7.3 Medical History

A summary of all medical history will be presented for the enrolled analysis set.

7.4 Treatment Compliance

Based on the IMP panel of the CRF, compliance in taking IMP is calculated by dividing the number of tablets taken by the total number of tablets the patients were scheduled to take during the study period. For lost-to-follow up patients, last IMP end date record will be used as the treatment end date. Treatment compliance will be summarized for the enrolled analysis set.

Protocol 405-201-00055 Statistical Analysis Plan

7.5 Prior and Concomitant Medications

The number and percentage of subjects taking concomitant medications will be tabulated by drug classification using the World Health Organization (WHO) drug dictionary for enrolled analysis set. Concomitant medications taken prior to start of treatment period and during treatment period will be summarized.

7.6 Protocol Deviation

Major protocol deviations will be summarized by type of deviation. In addition, a subject listing will be provided describing the deviations for each subject.

7.7 Smoking History

Smoking history will be summarized using descriptive statistics and reported for enrolled analysis set.

7.8 CCI

CCI

8 Efficacy Analysis**8.1 Primary Efficacy Endpoint**

The primary outcome variable is four-week continuous smoking abstinence rate during Week 4 to Week 7.

8.1.1 Primary Efficacy Analyses

The primary endpoint with the treatment of centanafadine is the four-week continuous abstinence rate of subjects during Week 4 to Week 7. A participant is considered abstinent from combustible cigarettes if he or she self-reports tobacco abstinence (no cigarette smoking, not even a puff) assessed by responses to daily messages throughout the period and has an exhaled CO level of less than 5 ppm using the Vitalograph Breath CO monitor in the office at scheduled Week 5 and Week 7. An intent-to-treat approach is

Protocol 405-201-00055 Statistical Analysis Plan

taken in which any participants lost to follow-up / early termination after receiving the IMP, or who have smoked during Week 4 to Week 7 will be counted as non-abstinent.

Primary endpoint calculation:

- Set it as four-week continuous abstinence:
 - If there is no smoking in the self-report.
 - And if subject has exhaled CO level of less than 5 ppm using the Vitalograph BreathCO monitor in the office at scheduled Week 5 or Week 7 value is missing.
 - And if subject has exhaled level of less than 5 ppm using the Vitalograph BreathCO monitor in the office at scheduled Week 7.
 - Missing value check:
 - For CO value, only one missing value is allowed, and Week 7 value cannot be missing.
 - For self-report value, only one missing in each visit Week (7 days) is allowed. The missing value is checked per each week.
- All the others will be set as non-abstinent.
 - Week 7 CO value is missing
 - Two or more missing in self-report in each visit week (7 days)
 - Lost to follow-up/Early termination
 - Subjects with actual data that they were smoking. (CO value \geq 5 ppm or any smoking record in self-report.)

A descriptive statistic will be provided for the continuous smoking abstinence rate during Week 4 to Week 7 with 90% binomial confidence intervals. For all binomial confidence intervals, it is based on normal approximation. If the number of abstinent or the number of non-abstinent ≤ 5 , we will use the exact method.

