8.1.2 Sensitivity Analysis I

Missing value is allowed. No need to check missing value. All the missing values during the treatment period will be considered as no-smoking.

Sensitivity analysis I endpoint calculation:

- Only subjects with adequate data that they were smoking during Week 4 to Week 7 are set as non-abstinent.
 - There is smoking in the self-report
 - Or subject has exhaled CO level of greater or equal to 5 ppm using the Vitalograph Breath CO monitor in the office at scheduled Week 5 and Week 7.

Protocol 405-201-00055 Statistical Analysis Plan

- Subjects lost to follow-up/Early termination will be set as non-abstinent.
- All other subjects having missing value in CO value and self-report will be set as abstinent.

A descriptive statistic will be provided with 90% binomial confidence intervals.

For all binomial confidence intervals, it is based on normal approximation. If the number of abstinent or the number of non-abstinent ≤ 5 , we will use the exact method.

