8.1.3 Sensitivity Analysis II

Two missing in self-report are allowed.

Sensitivity Analysis II endpoint calculation:

- Set it as four-week continuous abstinence:
 - If there is no smoking in the self-report.
 - And if subject has exhaled CO level of less than 5 ppm using the Vitalograph BreathCO monitor in the office at scheduled Week 5 or Week 5 value is missing.
 - And if subject has exhaled CO level of less than 5 ppm using the Vitalograph BreathCO monitor in the office at scheduled week 7
 - Missing value check:
 - For CO value, only one missing value is allowed, and Week 7 value cannot be missing.
 - For self-report value, only two missing in each visit week (7 days) is allowed.
- All the others will be set as non-abstinent.
 - Week 7 CO value is missing.
 - Three or more missing in Self-report every visit week (7 days)
 - Lost to follow-up/Early termination
 - Subjects with adequate data that they were smoking

A descriptive statistic will be provided with 90% binomial confidence intervals.

For all binomial confidence intervals, it is based on normal approximation. If the number of abstinent or the number of non-abstinent ≤ 5 , we will use the exact method.

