8.1.4 Sensitivity Analysis III

Three missing in self-report are allowed.

Sensitivity Analysis III endpoint calculation:

Protocol 405-201-00055 Statistical Analysis Plan

- Set it as four-week continuous abstinence:
 - If there is no smoking in the self-report.
 - And subject has exhaled CO level of less than 5 ppm using the Vitalograph BreathCO monitor in the office at scheduled Week 5 & Week 7
 - Missing value check:
 - For CO value, only one missing value is allowed, and Week 7 value cannot be missing.
 - For self-report value, only three missing in every visit week (7 days) is allowed.
- All the others will be set as non-abstinent.
 - Week 7 CO value is missing.
 - Four or more missing in self-report every visit week (7 days)
 - Lost to follow-up/Early termination
 - Subjects with adequate data that they were smoking

A descriptive statistic will be provided with 90% binomial confidence intervals.

For all binomial confidence intervals, it is based on normal approximation. If the number of abstinent or the number of non-abstinent ≤ 5 , we will use the exact method.

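### SAP 8.1.1: the second CO criterion for the primary endpoint names Week 7 where Week 5 is evidently meant, and so contradicts the section's own missing-value check

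*SAP*

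**What the plan says.** **SAP 8.1.1 (primary endpoint).** The narrative asks for CO "less than 5 ppm using the Vitalograph Breath CO monitor in the office at scheduled Week 5 and Week 7". The calculation block then requires three things: no smoking in the diary; a CO below 5 ppm "in the office at scheduled Week 5 or Week 7 value is missing"; and a CO below 5 ppm at Week 7. Its missing-value check reads "For CO value, only one missing value is allowed, and Week 7 value cannot be missing". Everyone else is non-abstinent. The list under that rule names a missing Week 7 CO but not a missing Week 5 CO, and it includes "Subjects with actual data that they were smoking", which it explains as a CO of 5 ppm or more or any diary record of smoking.

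**SAP 8.1.3 (Sensitivity II).** The parallel criterion reads "in the office at scheduled Week 5 or Week 5 value is missing", with the same CO check.

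**SAP 8.1.4 (Sensitivity III).** CO must be below 5 ppm "in the office at scheduled Week 5 & Week 7", again with the check that excuses a missing Week 5 value.

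**SAP 8.1.2 (Sensitivity I).** The governing line is "Only subjects with adequate data that they were smoking during Week 4 to Week 7 are set as non-abstinent". The CO line makes a participant non-abstinent on a CO "greater or equal to 5 ppm using the Vitalograph Breath CO monitor in the office at scheduled Week 5 and Week 7".

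**Protocol.** The synopsis requires CO below 5 ppm at Visits 5 and 6 (Weeks 5 and 7). Section 2.1 names week 7 only. Section 11.3.1 asks for CO confirmation at each time point.

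**The concern.** The second criterion of 8.1.1 contains a clause that cannot take effect, and the check below it allows a pattern that the criteria exclude. The SAP states no order of precedence between them. The primary numerator then depends on which part the programmer codes, in an open-label single-arm study whose rate is to be set against a 50% varenicline benchmark (protocol 1.1 and 11.2).

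Two sensitivity analyses have related but weaker wording problems. If the 8.1.4 condition is coded without its check, Sensitivity III is stricter than II on CO while looser on the diary, so a difference between them no longer reflects the diary allowance alone. If the CO line of 8.1.2 is coded as needing both readings to be high, a participant with one observed reading of 5 ppm or more stays out of the smoking group. The contrast with the primary analysis then mixes reversed positive tests with missing-data handling.

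**Working it through.** **Logic of 8.1.1.** Write W5 and W7 for the two CO readings, each below 5 ppm (<5), 5 ppm or more (≥5), or missing (M). Assume a complete smoke-free diary and no loss to follow-up or early termination.

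- Criteria as printed: (W5 <5 or W7 missing) and W7 <5. W7 cannot be both missing and <5, so this reduces to W5 <5 and W7 <5.
- Check plus non-abstinent list: W7 present and no observed reading ≥5. This is (W5 <5 or W5 missing) and W7 <5.

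**All 9 patterns** (A = abstinent, N = not counted as abstinent):

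| W5 | W7 | 8.1.1 criteria | 8.1.1 check and list | 8.1.3 | 8.1.4 condition alone | 8.1.4 with check | 8.1.2 both high | 8.1.2 either high |
|---|---|---|---|---|---|---|---|---|
| <5 | <5 | A | A | A | A | A | A | A |
| <5 | ≥5 | N | N | N | N | N | A | N |
| <5 | M | N | N | N | N | N | A | A |
| ≥5 | <5 | N | N | N | N | N | A | N |
| ≥5 | ≥5 | N | N | N | N | N | N | N |
| ≥5 | M | N | N | N | N | N | A | N |
| M | <5 | **N** | **A** | A | **N** | **A** | A | A |
| M | ≥5 | N | N | N | N | N | A | N |
| M | M | N | N | N | N | N | A | A |

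The two readings of 8.1.1 differ in 1 of 9 patterns (Week 5 missing, Week 7 <5), and 8.1.4 differs in the same one. The two readings of 8.1.2 differ in the 4 patterns with exactly one reading ≥5. These are patterns, not participants. With Week 5 in place of Week 7 in the missing clause, the 8.1.1 criteria and check agree in all 9.

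**Size at n=50.** The plan's own figure first: SAP Table 4-1 gives 0.37625 to 0.62375 for a rate of 0.50. Clopper-Pearson exact 90% limits with x=25 and n=50 reproduce this to five decimals. The analysis itself uses the normal approximation when both counts exceed 5: p ± 1.645 × √(p(1−p)/50).

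- For 25/50: 0.50 ± 1.645 × √(0.25/50) = 0.50 ± 0.116, or 0.384 to 0.616.
- Each reclassified participant changes the rate by 1/50 = 0.02.

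The documents give no rate of missing Week 5 readings, so the number affected is an assumption. Starting from 25/50 under the check, the literal criteria would give:

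| Affected (assumed) | Abstinent | Rate | 90% interval |
|---|---|---|---|
| 0 | 25/50 | 0.50 | 0.384 to 0.616 |
| 1 | 24/50 | 0.48 | 0.364 to 0.596 |
| 3 | 22/50 | 0.44 | 0.325 to 0.555 |
| 5 | 20/50 | 0.40 | 0.286 to 0.514 |

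**Evidence on intent.** For the allowance:

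- The check in 8.1.1 has no content unless it excuses Week 5.
- 8.1.3 prints the criterion consistently.
- 8.3.7, where both readings are wanted, says so and lists a missing value at either week as non-abstinent.
- 8.3.6 states a bare CO condition and then lets its check excuse a missing value, so checks in this SAP act as exceptions to conditions.

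Against it: the 8.1.1 narrative and the protocol synopsis name both visits.

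**The case against.** The strongest reply is that this is a wrong week number whose correction is plain from the SAP. The check, 8.1.3 and 8.3.7 all point to Week 5. The narrative is weak counter-evidence: it also speaks of diary responses over the whole period, yet the check tolerates one missing diary day per week. It states the concept, and the calculation block supplies the exceptions. Most of this stands. A reader might infer that the primary endpoint is undefined or that the sponsor's intent is wholly open; the documents do not support that. What remains is that the printed criterion, coded as it stands, gives the wrong classification for one pattern of the primary endpoint.

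A reader might also give 8.1.4 and 8.1.2 equal weight. They do not deserve it. By the convention of 8.3.6, the check in 8.1.4 can be read as an exception to its condition. In 8.1.2 the joint reading goes against the section's governing line and against the 8.1.1 rule that a CO of 5 ppm or more is smoking. It would also leave complete pairs with one high reading in neither group, because the closing line covers only participants with missing values.

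Finally, a reader might infer that one participant could decide the trial, since the lower 90% limit is 0.507 at 31/50 and 0.486 at 30/50. The documents state no interval rule for the 50% benchmark, and SAP 8.1.1 plans only a descriptive rate with an interval. That example illustrates sensitivity and shows no changed conclusion.

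**Conclusion.** The point holds as an error of wording in the primary endpoint rule. The second criterion of SAP 8.1.1 names the wrong week, cannot operate beside the third, and contradicts the section's own check and non-abstinent list for a participant with a smoke-free diary, a missing Week 5 CO and a Week 7 CO below 5 ppm. The SAP as a whole indicates that such a participant is meant to be abstinent, subject to the sponsor confirming this against the narrative and the synopsis.

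The effect is 2 points per affected participant, assuming 50 participants in the Full Analysis Set. The number affected is unknown and may be zero, and shifts of one or two participants are small against a half-width of about 0.116. It should be corrected before analysis because it concerns the primary numerator and costs little. The changes to 8.1.4 and 8.1.2 are alignment of wording and secondary.

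**What to change.** Before the data are analysed:

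1. In the second criterion of SAP 8.1.1, change Week 7 to Week 5 in the missing-value clause, as 8.1.3 has it.
2. Give 8.1.4 the CO wording of 8.1.3, so that the primary analysis and Sensitivity II and III differ only in the diary allowance.
3. In the CO line of 8.1.2, join the two weeks with or instead of and, so that any observed CO of 5 ppm or more counts as smoking.
4. Add the Week 5 exception to the 8.1.1 narrative. Replace the present entry of none in SAP section 14 with a note that the rule departs from the protocol synopsis, and that the synopsis, protocol 2.1 and protocol 11.3.1 state the CO requirement differently.

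If the sponsor instead intends both readings to be required, remove the missing clause from the criteria in 8.1.1 and 8.1.3 and the one-missing CO allowance from the checks in 8.1.1, 8.1.3 and 8.1.4.

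The cost is one sponsor confirmation, a few wording edits and, if the allowance is kept, one section 14 entry. No new data or analyses are needed.

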Given the conditional logic of the phase one analyses, Monte Carlo simulations based on a sample size of 50 were conducted to determine the significance thresholds for the binomial tests so that the overall Type I error rate across all tests would be 10% (9.87% of 100,000 simulated datasets), assuming the null hypothesis that centanafadine yields a four-week continuous smoking abstinence rate of 50% and an overall incidence of nausea of 30%. The power of the phase one analyses (probability of moving to phase two) was also determined by Monte Carlo simulations for three scenarios. In the first scenario, the treatment has a higher four-week continuous abstinence rate at 6 weeks post target quit date (65%) than varenicline, but an equivalent rate of nausea (30%). Power under this scenario is about 74%. In the second scenario, the treatment has the same four-week continuous abstinence rate at 6 weeks post target quit date as varenicline (50%) but has a lower nausea rate (15%). Power under this scenario is about 76%. Last, if the treatment generates both a higher four-week continuous abstinence rate at 6 weeks post target quit date (65%) and a lower rate of nausea (15%) then power is about 94%.

STATISTICAL METHODS

The estimation of the four-week continuous smoking abstinence rate at 6 weeks post target quit date is around 50% and 30% of treated individuals experiencing nausea from varenicline treatment based on the historical studies.² The smoking abstinence rate during weeks 4-7 will be calculated with 90% binomial confidence intervals, and the incidence rate of nausea will be tabulated, which will be compared with the thresholds established for efficacy and tolerability.

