2.2 SECONDARY OBJECTIVE: REDUCTION IN INCIDENCE OF NAUSEA

A secondary objective will be to determine if centanafadine yields equivalent efficacy to that of varenicline), with a significant reduction in the incidence of nausea, the most prevalent side effect reported following varenicline treatment.

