11.1 SAMPLE SIZE ESTIMATION

CCI

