11.2 STATISTICAL METHODS

The estimation of the four-week continuous smoking abstinence rate at 6 weeks post target quit date is around 50% and 30% of treated individuals experiencing nausea from varenicline treatment based on the historical studies.² The smoking abstinence rate during weeks 4-7 will be calculated with 90% binomial confidence intervals, and the incidence rate of nausea will be tabulated, which will be compared with the thresholds established for efficacy and tolerability.

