Protocol 405-201-00055 Statistical Analysis Plan

11	Pharmacodynamic Analyses.....	24
12	Pharmacogenomic Analyses.....	24
13	Interim Analysis	24
14	Changes in the Planned Analyses	25
15	References	26
16	Potential Clinical Relevance Criteria	27
17	Proposed List of Summary Tables and Listings.....	30

Protocol 405-201-00055 Statistical Analysis Plan

List of Appendices

Appendix 1	Criteria for Identifying Vital Signs and Weight of Potential Clinical Relevance	27
Appendix 2	Criteria for Identifying Laboratory Values of Potential Clinical Relevance	28
Appendix 3	Criteria for Identifying ECG Measurements of Potential Clinical Relevance	29

Protocol 405-201-00055 Statistical Analysis Plan

List of In-text Tables

Table 4-1	90% Confidence Interval for Sample Size of 50 Subjects.....	11
Table 5.4-1	Mapped Trial Week Windows for Efficacy Analysis.....	12

Protocol 405-201-00055 Statistical Analysis Plan

List of In-text Figures

Figure 3.1-1	Trial Design Schematic.....	10
--------------	-----------------------------	----

Protocol 405-201-00055 Statistical Analysis Plan

List of Abbreviations and Definition of Terms

Abbreviation	Definition
AE	Adverse event
AESI	Adverse events of special interest
ALP	Alkaline phosphatase
ALT	Alanine aminotransferase
AST	Aspartate aminotransferase
BID	Twice daily
BMI	Body mass index
CRF	Case report form
CO	Carbon monoxide
CCI	
ECG	Electrocardiogram
ICF	Informed consent form
ICH	International Conference on Harmonisation
IEC	Independent ethics committee
IMP	Investigational medicinal product
IND	Investigative new drug
MedDRA	Medical Dictionary for Regulatory Activities
MHI	Medication handling irregularity
PE	Physical examination
SAE	Serious adverse event
SAP	Statistical analysis plan
TDD	Total daily dose
TEAE	Treatment-emergent adverse event
ULN	Upper limit of normal
WHO	World health organization

Protocol 405-201-00055 Statistical Analysis Plan

1 Introduction

This statistical analysis plan (SAP) describes the statistical methodology and data analysis algorithms and conventions to be applied for statistical analysis and reporting of data collected under the clinical protocol 405-201-00055. The SAP is consistent with latest version of protocol version 3.0 dated on 16 August 2021.

2 Study Objectives

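### The SAP does not implement or cite the protocol's two-endpoint decision rule, so the stated 9.87% type I error and 74/76/94% power do not describe the SAP's own analysis

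*SAP*

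**What the plan says.** **Protocol.** The Sample Size Estimation paragraph of the synopsis describes a conditional procedure on two endpoints. It says that "Monte Carlo simulations based on a sample size of 50 were conducted to determine the significance thresholds for the binomial tests". The target for those thresholds is worded as follows: "the overall Type I error rate across all tests would be 10% (9.87% of 100,000 simulated datasets"). The null values behind that target are 50% for abstinence and 30% for nausea. The paragraph then gives power, defined as the chance of moving to phase two, for three scenarios:

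- 65% abstinence with 30% nausea: about 74%
- 50% abstinence with 15% nausea: about 76%
- 65% abstinence with 15% nausea: about 94%

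Protocol 11.2 plans a 90% binomial interval for abstinence and a tabulated nausea rate, "which will be compared with the thresholds established for efficacy and tolerability". Protocol 11.1, the body section on sample size, is redacted. Protocol 11.3 leaves analysis details to the SAP. Protocol 2.2 asks for efficacy equivalent to varenicline "with a significant reduction in the incidence of nausea".

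**SAP.** Section 4 presents Table 4-1, which gives 90% limits for 50 subjects at rates of 0.3, 0.4, 0.45 and 0.5. It names no null value, test, error rate or power. Section 8.1.1 states: "A descriptive statistic will be provided for the continuous smoking abstinence rate during Week 4 to Week 7 with 90% binomial confidence intervals". It specifies the normal approximation, switching to the exact method when either count is 5 or fewer. Section 8.2.1 reports nausea as a count and percentage. The objectives in 2.1 and 2.2 remain comparative: superior abstinence, then equivalent efficacy with less nausea. Section 1 asserts that "The SAP is consistent with latest version of protocol version 3.0 dated on 16 August 2021", and section 14 records no changes to the planned analyses.

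**The concern.** The protocol's error rate and power belong to a rule that uses both endpoints. The SAP, which should turn that rule into an analysis, contains only estimates, with no reference value to judge them by and no pointer to where the rule is written. An analyst working from the SAP would report an abstinence interval and a nausea percentage without a written step from those numbers to superior or equivalent. In a single-arm, open-label trial judged against historical rates, the rule fixed in advance is the main protection against deciding what counts as success after seeing the results.

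The nausea side is the more exposed. The protocol's second scenario assumes abstinence no better than the benchmark, so its 76% power must come almost wholly from nausea. That is the endpoint for which the SAP plans no inferential output.

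The interval method is a second, smaller mismatch: the precision displayed in section 4 is not that of the method specified in 8.1.1.

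**Working it through.** **Inputs.** From the protocol synopsis: n = 50; null rates 0.50 (abstinence) and 0.30 (nausea); alternatives 0.65 and 0.15; 9.87% from 100,000 simulations; power 74/76/94%. From SAP 4 and 8.1.1: Table 4-1 and the normal-approximation method. Let X be the number abstinent and N the number with nausea, both binomial. I assume X and N are independent.

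**1. Can a rule of the protocol's kind give its figures?** The readable text gives no cut-offs, so I searched rules of the form: success if X ≥ r1, or if r2 ≤ X < r1 and N ≤ c. Success probability = P(X ≥ r1) + P(r2 ≤ X < r1) × P(N ≤ c). The closest fit is r1 = 31, r2 = 20, c = 9:

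| True rates (abstinence / nausea) | Calculation | Result | Protocol |
|---|---|---|---|
| 50% / 30% | 0.0595 + 0.8811 × 0.0402 | 9.49% | 9.87% |
| 65% / 30% | 0.7264 + 0.2735 × 0.0402 | 73.7% | 74% |
| 50% / 15% | 0.0595 + 0.8811 × 0.7911 | 75.7% | 76% |
| 65% / 15% | 0.7264 + 0.2735 × 0.7911 | 94.3% | 94% |

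The three powers are attainable with a two-endpoint rule. The type I error is not matched: the simulation standard error is √(0.0987 × 0.9013 / 100,000) = 0.094 percentage points, so the gap of 0.38 points is about four standard errors. The sponsor's actual rule therefore remains unknown. In the second scenario the abstinence branch contributes 5.95 of the 75.7 points.

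**2. What the SAP's abstinence interval would give alone.** Suppose success meant that the lower 90% limit exceeds 0.50. Neither document says so; this is my assumption. The normal-approximation limit is p − 1.645 × √(p(1−p)/50):

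- 30/50: 0.600 − 0.114 = 0.486
- 31/50: 0.620 − 0.113 = 0.507

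The cut-off is therefore 31. P(X ≥ 31 | 0.50) = 5.95% and P(X ≥ 31 | 0.65) = 72.6%. Power in the three scenarios is 72.6%, 5.95% and 72.6%, against 74%, 76% and 94%. The exact method needs 32/50 (lower limit 0.514) and gives 3.25% error and 62.2%, 3.25% and 62.2% power.

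**3. Table 4-1 against 8.1.1.** Exact (Clopper-Pearson) limits are Beta(0.05; x, n−x+1) and Beta(0.95; x+1, n−x).

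| Rate | Table 4-1 | Exact | Normal approximation |
|---|---|---|---|
| 0.30 | 0.19488-0.42373 | 0.19488-0.42373 | 0.1934-0.4066 |
| 0.40 | 0.28313-0.52612 | 0.28313-0.52612 | 0.2860-0.5140 |
| 0.45 | 0.32912-0.5755 | 0.32912-0.57550 | 0.3343-0.5657 |
| 0.50 | 0.37625-0.62375 | 0.37625-0.62375 | 0.3837-0.6163 |

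All four rows are exact. The switch in 8.1.1 to the exact method does not reach them, because their counts run from 15 to 25.

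**4. Would intervals for both endpoints be a safe substitute for the rule?** The normal-approximation upper limit for nausea falls below 0.30 at 10/50 (0.293) but not at 11/50 (0.316), and P(N ≤ 10 | 0.30) = 0.0789. Declaring success on X ≥ 31 or N ≤ 10 gives 1 − (1 − 0.0595)(1 − 0.0789) = 13.4% overall error. Counting nausea only when 20 to 30 are abstinent (the floor inferred in step 1) gives 0.0595 + 0.8811 × 0.0789 = 12.9%. Both exceed the protocol's 10%.

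**The case against.** The strongest reply is that the two documents should be read together. Protocol 11.2 still requires the comparison with thresholds, the SAP produces both counts that a count-based rule needs, and SAP section 1 declares consistency with the protocol. Protocol 11.3 also foresees descriptive statistics, and the outputs named in 11.2 are those the SAP supplies. All of this stands. It limits the point to the SAP's failure to state or cite the rule and shows that a descriptive abstinence interval is not in itself a departure. It does not close the gap: a general consistency sentence names no benchmark or cut-off, and the readable text does not define equivalent efficacy.

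A reader might infer that the thresholds were never set, or that the plan as a whole has no basis for judging nausea. The documents do not support that: the synopsis says thresholds were simulated, and the full rule may be in redacted 11.1. Nor does the 9.49% in step 1 show that 9.87% is wrong, because it comes from guessed cut-offs.

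A reader might also infer that the choice of interval method would reverse the trial's conclusion, since at 31/50 the lower limit is 0.507 by normal approximation and 0.494 exactly. Neither document says that the interval is read against 50%, and a count threshold would not depend on the interval method.

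**Conclusion.** The point holds as a gap in the SAP. The 9.87% error and 74/76/94% power describe a conditional two-endpoint rule that SAP 4, 8.1.1 and 8.2.1 neither apply nor cite, while the SAP keeps comparative objectives and reports no changes. The largest shortfall is in the second scenario, where the abstinence interval read alone would have about 6% power against the stated 76%. That figure assumes the interval is read against 50%; the reconstruction in step 1 and the combined error rates in step 4 assume independent endpoints. The mismatch between Table 4-1 and 8.1.1 is certain but small: at 25/50 the width is 0.248 in the table and 0.233 under the specified method.

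This should be fixed, but it does not undermine the design. The protocol's comparison remains in force, and the study is a small exploratory phase 2 trial.

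**What to change.** 1. In SAP 8.1.1 and 8.2.1, state the 50% and 30% benchmarks and carry over, or cite by section number, the simulated count thresholds and the conditional rule. Say what equivalent efficacy means within the rule, and how the thresholds apply if the Full Analysis Set is not exactly 50. Make this rule the only basis for declaring success.
2. Use the exact (Clopper-Pearson) method in both Table 4-1 and 8.1.1, and in the other sections that repeat the 8.1.1 wording. The price is slightly wider intervals.
3. Add a 90% exact interval for nausea as a descriptive output. It should not become a second decision criterion, given the roughly 13% error found in step 4 for normal-approximation interval cut-offs.

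These changes cost SAP text and one extra interval; the sponsor reports having already simulated the thresholds. No new data or participants are needed.

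If only estimation is intended, the alternative is to withdraw the error and power figures and reword the objectives as estimation against the fixed benchmarks. That costs more: it needs a protocol amendment with IRB approval (Protocol 12.1) as well as an entry in SAP section 14.
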